Previous studies have indicated that with surfactant *instillation* a minimum of 19 mg lipid/kg natural surfactant was required to improve gas exchange and 53 mg lipid/kg resulted in greater improvement in pressure-volume curves in PT lambs¹⁵. Consequently, an empiric dose of 50 mg/kg has been accepted as the minimal amount of surfactant required to effectively treat neonates with RDS although most centers use 100 mg/kg¹⁶, a dose that exceeds ten-fold the amount necessary to establish a monolayer. On the other hand, pharmacokinetic and clinical data suggest that 200 mg PL/kg of instilled surfactant has a longer half-life and a better acute response compared to 100 mg/kg^{17,18}. Therefore both these doses will be tested in this Phase I/II trial. Several investigators have shown that even quite low amounts of inhaled surfactant might be more effective in improving gas exchange than large amounts of instilled substance¹⁹⁻²³.

Initial reports evaluating *aerosolized* surfactant in lung injury demonstrated significant improvements in oxygenation with as little as 0.5 -2 mg/kg surfactant deposited in lung tissue¹⁹. This is lower than the endogenous surfactant pool size of 3-4 mg/kg that is required to increase compliance in PT rabbits²⁴ and is comparable to the theoretical dose of 3 mg/kg that would be necessary to form a monomolecular film on the alveolar surface^{25,26}. As surfactant delivery techniques have improved, the deposition efficiency has increased. In one study, 31% of the total quantity of surfactant aerosolized into the system was deposited in lung tissue

representing a lung dose of 4.5 mg lipid/kg²⁷. Furthermore, a dose-response relationship existed for AS in this model. There is *in vitro* evidence that even with lower alveolar delivery with aerosolized as compared to instilled surfactant, surfactant retains its anti-inflammatory properties and actually decreases leukocyte infiltration in the alveolus and the interstitium and improves oxygenation²⁸. Our Preliminary data and reports in literature suggest that diluted surfactant solutions are most favorable for aerosolisation (Section 3.4.1 & 3.4.2)^{19,29-32}.

Based on the above, we will evaluate two doses and dilutions of Survanta:

1. Dosing Schedule I: Survanta 4 ml (or 100 mg PL)/kg + equal volume of NS
2. Dosing Schedule II: Survanta 4 ml (or 100 mg PL)/kg + 2x volume of NS
3. Dosing Schedule III: Survanta 8 ml (or 200 mg PL)/kg + equal volume of NS

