4. Dosing Schedule IV: Survanta 8 ml (or 200 mg PL)/kg + 2x volume of NS

1.1.4.4. Administration of Aerosolized Survanta:

a) Aerosol Generating Device:

Our goal is to study safety and feasibility of AS; optimal dose and dilution; and to get an estimate of efficacy of AS using existing modes of NIV and aerosol delivery. We do not mandate the mode/manufacturer of NIV or the aerosol generating device used in the study as there is no evidence of significant differences in outcomes among various commercial devices approved for use in infants; we will record the mode of NIV and nebulizer type to be able to evaluate safety, feasibility and associations with response. The MH jet and VM nebulizers are FDA-approved for use in infants, and have been shown to be efficacious in delivery of AS; this is supported by our preliminary data. The operating characteristics of the nebulizers are different – the VM nebulizer puts out more aerosol in a shorter period of time which may result in a quicker response and may be better tolerated by the patient and bedside caregivers; however this may be associated with increased condensation in the NIV circuit and delivery of only part of the surfactant placed in the reservoir. In addition the VM nebulizer has a tendency to stop because of clogging of pores by viscous surfactant. This can be remedied by tapping the nebulizer or using more dilute surfactant. In contrast to the VM nebulizer, the MH jet nebulizes the surfactant placed in the nebulizer slowly, resulting in a lower output compared to the VM nebulizer; less condensation in NIV circuit and a more prolonged period of aerosol delivery. This may lead to slower onset of action and also impact its acceptance by bedside nurses and respiratory therapists.

b) Non-Invasive Ventilator Circuit:

Non-invasive respiratory support, defined as any form of respiratory support that is not delivered via an endotracheal tube, will include NCPAP, NIPPV, and HFNC for this study. *Studies have shown that the commercial system of delivering NIV is of little importance, short binasal prongs are a better interface than single longer prongs, and that there is no difference between NIPPV or HFNC compared to CPAP*^{7,33-41}.

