At our institution, as demonstrated by our preliminary data (Section 3.4.5), NIPPV and NCPAP are the modes of NIV used for primary respiratory support in infants ≤ 32 weeks GA; and NCPAP and HFNC as primary modes of respiratory support in PT infants >32 weeks GA. A common ventilator circuit is used for NIPPV and NCPAP with short binasal prongs as the patient interface (INCA®). For HFNC, the Fisher & Paykel heated humidified system is used with short binasal prongs.

The neonatal ventilator circuit will have heated and humidified gas flow as is standard of clinical care. The *MiniHeart Lo-Flo jet nebulizer (WestMed®)* will be placed in the inspiratory limb of the ventilator circuit close to the patient interface wherever there is a natural break in the circuit. The gas flow in the nebulizer will be ≤ 2 LPM and will have the same FiO₂ as the NIV circuit. The output of this nebulizer is 8 ml/hr at a flow rate of 2 LPM. After the flow from the nebulizer is introduced, the ventilator parameters and or gas flow through the ventilator will be adjusted to keep pressures constant. Every attempt will be made not to change ventilator settings during nebulization unless patient's well-being mandates it. The *AeroNeb Solo nebulizer (Aerogen®)* will be placed in the ventilator circuit close to the patient interface wherever there is a natural break. Although in pediatric and adult MV, vibrating mesh nebulizer placement proximal to the humidifier was associated with increased aerosol delivery⁵⁴, during NIV in pediatric and infant models, aerosol delivery was greater if the nebulizer device was placed closer to the patient interface^{55,56}.

Surfactant dose determined from the Dosing Schedule Table (Appendix IV) will be diluted with saline, mixed by a gentle swirling motion and placed in the nebulizer chamber and aerosolized till the nebulizer runs dry. If the volume is in excess of the capacity of the nebulizer reservoir, the reservoir will be replenished as the level of medication drops in the reservoir by research staff at the bedside or using a syringe pump to deliver the dose depending upon availability. Inspiratory and expiratory tubes will be kept at a lower level than the nasal prongs to prevent reflux of condensed fluid from these tubes into the nasal prongs^{30,57}.

c) Patient Interface:

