Only short binasal prongs will be used for aerosol delivery in the NIV circuit. Since the ventilator circuit for NCPAP and NIPPV is identical, only one type of neonatal nasal prongs (INCA®) will be used. For the HFNC circuit, only the neonatal Fisher & Paykel short binasal prongs will be used. Nasal cannulas will be applied with recommendations that the prong outer diameter occupy $\sim 50\%$ of the nares internal diameter to allow free egress of flow around the cannula³⁴.

d) Number of doses of Aerosolized Surfactant & Intervals between Doses:

Infants will be eligible to receive a 2nd dose of AS 4 hours after the 1st dose of AS if there is continued need for NIV with FiO₂ $\geq 25\%$ or PEEP ≥ 4 cmH₂O or HFNC rate ≥ 2 LPM.

Since most PT infants with RDS receive ≤ 2 doses of intratracheal surfactant as standard of care, we chose 2 doses of AS as being the minimum number to assess efficacy without inordinately delaying standard of care treatment with intratracheal surfactant⁵⁸. Early trials of intratracheal surfactant used dosing intervals ranging from 1 to 12 hours based on ventilator settings. Since pulmonary delivery following aerosolisation is not precisely quantified, we will administer the 2nd dose 4 hours after the 1st if the infant meets criteria.

e) Duration of nebulization:

Time to nebulize each dose will depend upon volume of diluted surfactant, type of nebulizer, and ambient humidity and temperature. It is expected that for each dose nebulization will be <1 hour for the smallest infants and $<4-5$ hours in the largest infants. This Phase II study will provide critical information regarding time for nebulization of various doses for PT babies and will be crucial in determining tolerance of intervention both by the patient and clinical bedside caregivers. This will be one factor in selecting the optimal dose and dilution of AS for the definitive Phase III trial.

1.1.4.5. Gestational Age Group Strata:

Enrolled infants will be stratified by three GA strata (24^{0/7}-28^{6/7}; 29^{0/7} - 32^{6/7}, 33^{0/7} - 36^{6/7}) because need for intubation and MV has been reported to be higher in more immature infants along with higher co-morbidities of prematurity and mortality. Infants <24 weeks will be excluded as most are likely to receive intubation. ^{59,60}

1.1.4.6. Randomization Procedures: Assignment to Surfactant dosing schedule:

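### Jet-nebulizer times implied by the plan's own figures exceed its single stated range on Schedules III and IV at plausible weights, and the AE windows that include them differ by schedule with no common-window analysis stated in the visible text

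*Combined protocol and SAP*

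**What the plan says.** Section 1.1.4.3 defines four schedules by Survanta volume and saline dilution, from "Dosing Schedule I: Survanta 4 ml (or 100 mg PL)/kg + equal volume of NS" to "Dosing Schedule IV: Survanta 8 ml (or 200 mg PL)/kg + 2x volume of NS". Schedules II and III lie between: 4 ml/kg with twice its volume of saline, and 8 ml/kg with an equal volume.

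For the MiniHeart jet, section 1.1.4.4 b) states: "The output of this nebulizer is 8 ml/hr at a flow rate of 2 LPM". Gas flow may not exceed 2 LPM. The diluted dose is "placed in the nebulizer chamber and aerosolized till the nebulizer runs dry". Table 10 puts half of each schedule on the jet and half on the AeroNeb. No output figure is given for the AeroNeb; section 1.1.4.4 a) says only that "the VM nebulizer puts out more aerosol in a shorter period of time".

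Section 1.1.4.4 e) then gives one expected duration, not split by schedule or nebulizer: "It is expected that for each dose nebulization will be <1 hour for the smallest infants", and under 4-5 hours for the largest. It adds that time depends on volume and nebulizer type, will be measured, and will be one factor in choosing the dose and dilution. On redosing, section 1.1.4.4 d) says: "Infants will be eligible to receive a 2nd dose of AS 4 hours after the 1st dose of AS".

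Section 1.1.9, items 3-6 (heart rate or blood pressure events needing treatment, desaturation or apnea, resuscitation, air leak), counts events while the intervention is given and for six hours after it. Section 1.1.12 (Aim #1) compares AEs across dose/dilution groups and nebulizers, and Aim #2 selects partly on the fewest adverse responses. Section 1.1.10 ranks the dose-safety relationship above dose-efficacy, and section 1.1.5 confirms that there is no placebo group.

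**The concern.** There are two linked problems. First, total volume differs threefold between Schedules I and IV, so at a fixed output one duration range cannot describe all four. Second, the window for AE items 3-6 contains the aerosol time and so ends later on a slower schedule. An event at the same hour after the start may count on a long schedule and not on a short one.

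With no placebo group to show the background rate of apnea, bradycardia and desaturation, a longer window also collects more background events. A higher count on a high-volume schedule could then reflect greater risk per hour, a longer administration, or both, and the count alone cannot say which. That matters because the AE comparison feeds the choice of schedule for Phase III. The comparison between nebulizers is affected in the same way, because one is described as faster.

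**Working it through.** **Inputs**
- Survanta per kg and saline ratio: section 1.1.4.3.
- Jet output 8 ml/hr at 2 LPM, whole volume nebulized: section 1.1.4.4 b). Output is assumed equal at both dilutions. If it falls at flows below 2 LPM, times are longer.
- Window for AE items 3-6: aerosol time plus 6 h (section 1.1.9).
- Body weight: not in the documents. 1, 2 and 3 kg are assumed, with 0.5-3.5 kg as the wider range.

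**Time per dose on the jet.** Hours per kg = Survanta ml/kg × (1 + saline ratio) / 8. Limiting weight = hours / (hours per kg).

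| Schedule | ml/kg | h/kg | Under 1 h only below | Reaches 4 h at | Reaches 5 h at |
|---|---|---|---|---|---|
| I | 4+4 = 8 | 1.0 | 1.00 kg | 4.00 kg | 5.00 kg |
| II | 4+8 = 12 | 1.5 | 0.67 kg | 2.67 kg | 3.33 kg |
| III | 8+8 = 16 | 2.0 | 0.50 kg | 2.00 kg | 2.50 kg |
| IV | 8+16 = 24 | 3.0 | 0.33 kg | 1.33 kg | 1.67 kg |

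The plan's range is reproduced for Schedule I over 0.5-3.5 kg, if the smallest infants are under 1 kg. Schedule II fits or is borderline. Schedules III and IV do not fit over that range: at 0.6 kg they take 1.2 and 1.8 h, and at 3 kg they take 6 and 9 h.

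**AE window, jet, one dose** = h/kg × weight + 6.

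| Weight | I | II | III | IV | IV/I |
|---|---|---|---|---|---|
| 1 kg | 7 h | 7.5 h | 8 h | 9 h | 1.29 |
| 2 kg | 8 h | 9 h | 10 h | 12 h | 1.50 |
| 3 kg | 9 h | 10.5 h | 12 h | 15 h | 1.67 |

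At 2 kg, an apnea 11 h after the start is inside the Schedule IV window and outside the other three.

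**Redosing.** If the second dose starts 4 h after the end of the first, two Schedule I doses at 2 kg span 2 + 4 + 2 + 6 = 14 h, longer than the 12 h for one Schedule IV dose. The order of the windows can therefore reverse.

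**What this could do to a proportion.** Illustration only: jet, 2 kg, one dose, equal constant hourly risk. The Schedule IV proportion is 1 − (1 − p)^(12/8), where p is the Schedule I proportion.
- Assumed p = 30%: 1 − 0.7^1.5 = 41.4%. If all risk falls after aerosol it stays at 30%; if all falls during aerosol it is 1 − 0.7^(6/2) = 65.7%.
- Assumed p = 5%: 1 − 0.95^1.5 = 7.4%. The excess of 2.4 points is 0.024 × 15 = 0.36 of an infant among the 15 per schedule and nebulizer in Table 10 (3 strata × 5). After the later increase (section 1.1.10), (220 − 20)/8 = 25 per cell if evenly spread, and the excess is 0.024 × 25 = 0.6 of an infant.

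**Second dose.** Counted from the start of the first dose, 4 h would pass with the jet still running above 1.33 kg (IV), 2.0 kg (III) and 2.67 kg (II). Counted from its end, there is no overlap.

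**The case against.** The strongest reply is that infants are randomized to whole schedules and duration is part of each schedule, so AE counts per administration are a valid comparison. The plan also recognises that duration varies and uses it in dose selection. This stands: the planned counts should be kept. It does not explain why an event at a given hour from the start should be eligible on one schedule and not on another.

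It is also fair that the duration statement is only an expectation, is to be measured, and enters no test or sample size. It needs correction, not redesign.

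Three stronger readings are tempting, and the documents do not support them.
- A reader might infer that no exposure-based safety analysis exists. Section 1.1.12 refers to mock Table M5 in Appendix IX, which is not visible. Table 9, though broken in extraction, appears to mark AEs to 72 h after the intervention, and section 1.1.4.10 follows vital signs to 72 h. Only the visible text can be said to lack such an analysis.
- A reader might infer a threefold difference in aerosol time between Schedules IV and I throughout. That holds only for the jet at equal flow and equal output across dilutions. Section 1.1.4.3 says that dilute solutions aerosolize best. On mesh clogging, section 1.1.4.4 a) says: "This can be remedied by tapping the nebulizer or using more dilute surfactant". The AeroNeb ratio is unknown.
- A reader might infer that second doses overlap first doses. This follows only if the 4 hours run from the start. Nasal trauma is timed from AS in section 1.1.4.10 and from the end of AS in section 1.1.9, which suggests that the shorter wording means the end.

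**Conclusion.** The point holds in a limited form, at minor to moderate severity. At the stated jet output, taken as constant, the single duration range does not hold on the jet for Schedule IV above 1.33-1.67 kg or Schedule III above 2.0-2.5 kg. That these weights occur in the trial is an assumption, and Appendix IV, the dosing table, is not visible.

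The part with consequence is the AE window. For items 3-6 it is 8, 9, 10 and 12 h on Schedules I-IV (jet, one dose, assumed 2 kg), it differs by nebulizer by an unknown amount, and it changes with redosing. Items 1, 2, 7 and 8 do not carry the six-hour tail.

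A reader might go further and infer that the safety comparison is invalid or that the wrong schedule will be chosen. The documents do not support that. The size of any distortion is unknown: section 1.1.12 expects AEs to be infrequent, and at an assumed 5% the illustrated excess is under one infant per cell. The supported conclusion is that a comparison on equal follow-up is a cheap gain that the visible text does not state.

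**What to change.** 1. Restate the expected nebulization time by schedule, nebulizer and weight, using observed times where available.
2. Keep the planned AE counts as the whole-schedule comparison. Beside them, report the proportion of infants with each item 3-6 event in one common window from the start of the first dose. The window should be long enough to contain the aerosol in every schedule, provided AE collection is confirmed to that point. If only 6 h is covered in every infant, state that this cuts off the aerosol on jet Schedule IV above 6/3 = 2 kg. Report second doses given inside the window.
3. Report events per infant-hour descriptively, during and after aerosol separately, by schedule and nebulizer, with confidence intervals clustered by infant because events can recur. State that these rates do not replace the counts.
4. Reconcile the nebulization times in section 1.1.4.4 e) with the second-dose wording in 1.1.4.4 d), stating whether the interval runs from the start or the end of the dose. No dose or interval is proposed here.

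The cost is a corrected statement, some SAP wording and one descriptive table. It needs aerosol start and stop times, which the promise to report nebulization times implies are recorded; the study forms are not visible. The table will be imprecise: 15 infants × 8 h = 120 infant-hours, and 5 events in that time is 4.2 per 100 h, exact 95% CI 1.4 to 9.7 before clustering. Hourly rates read alone could also flatter a long schedule.

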**AEROSOLIZED SURVANTA IN NEONATAL RESPIRATORY DISTRESS SYNDROME:
PHASE I/II STUDY (IND 115430)**

NCT02294630

FINAL STUDY PROTOCOL & STATISTICAL ANALYSIS PLAN

Date of last Revision: 07-31-2017

RESEARCH STRATEGY

1.1. Research Design:

1.1.1. Study Design:

This is a proposal for the Phase II portion of our unblinded Phase I/II trial^{1,2}. It is a safety, feasibility and dose finding study of AS for the treatment of RDS in spontaneously breathing PT neonates receiving NIV. To remove selection bias and control temporal trends, infants will be randomized to 4 parallel fixed dosing schedule groups^{1,2}. This Phase II study will identify 1 or 2 optimal doses, and provide additional data for safety, feasibility and early indication of efficacy that will be the basis for designing a definitive Phase III trial. Optimal dose(s) will be identified based on evidence of a significant positive trend with increasing dose, even if no two groups are significantly different^{3,4}. Equitable representation of GAs within each dose group will be achieved by stratified randomization. Equitable representation of two FDA-approved nebulizers will be achieved by using block sizes of 8. It is expected that choice of nebulizer device will not affect efficacy but may influence caregiver preference based on institutional practice and ease of administration (feasibility).

1.1.2. Inclusion Criteria:

1. Infants admitted to the NICU at Hutzel Women's Hospital (HWH)/Children's Hospital of Michigan (CHM)
2. Gestational age of 24^{0/7}-36^{6/7} weeks
3. Postnatal age \leq 24 hours
4. Clinical diagnosis of RDS based on (i) presence of at least two of the four classic symptoms (need of supplemental oxygen, tachypnea, intercostal retractions or grunting), *and* (ii) exclusion of other causes of respiratory failure (Section 3.6.4.1) *and* (iii) Clinician intent to administer surfactant if infant requires intubation
5. Respiratory support with NIV (CPAP or NIPPV or HFNC) with FiO₂ \geq 25% or PEEP \geq 4 cmH₂O or HFNC rate \geq 2 LPM for \leq 8 hours
6. Written informed consent from parent/guardian

1.1.3. Exclusion Criteria:

1. Previous receipt of surfactant
2. Infants with respiratory distress who are unstable and require immediate intubation (Section 3.6.5)
3. Active air leak syndrome (e.g. pneumothorax, pneumomediastinum)
4. Lethal congenital malformations; death anticipated within first 3 days of life; decision to withhold support

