5. Serious abdominal, cardiac, airway or respiratory malformations including tracheal esophageal fistula, intestinal atresia, omphalocele, gastroschisis, pulmonary hypoplasia, or diaphragmatic hernia
6. Neuromuscular disorder resulting in respiratory compromise

1.1.4. Study Procedures:

Table 9: Time & Event Table:

Assessment	Screening	Baseline	Treatment	Post-intervention Events						
				0-24 hrs	0-24 hrs	0-24 hrs	0-72 hrs post intervention	D7	D14	D28
Informed consent	x									
History	x									
Vital Signs	x	x	x	x						
CRIB score		x								
RD score		x	x	x						
Nasal Trauma Score		x	x	x						
Blood gas	x	x	x	x						
Cerebral oximetry		x	x	x						
Gastric aspirate		x		x						
Effectiveness:										
Primary outcome				x						
Secondary outcome				x	x	x	x	x		x
Safety:										
Adverse events			x	x						

Feasibility:					X				
---------------------	--	--	--	--	---	--	--	--	--

CRIB-Clinical Risk Index for Babies; RD – respiratory distress; D7 = 7 days, D14 = 14 days, D28 = 28 days

Study procedures are described below and their time frame is summarized in Table 9; greater detail is provided in the *drafts* of the standard operating procedures (Appendix VII) and study forms (Appendix VIII).

1.1.4.1. Ascertainment of Study Eligibility:

Research staff will screen admission databases at HWH and CHM NICU for infants 24^{0/7} to 36^{6/7} weeks GA admitted at ≤ 24 hours of age for study eligibility and maintain a screening log. Informed parental consent will be sought for study participation of potentially eligible infants after a member of the clinical team obtains permission for research staff to approach the parent(s) (Appendix V). To minimize treatment delays, attempts will be made to obtain consent antenatally or soon after admission. Once the clinical team initiates NIV in a potentially eligible infant, the research team will determine that all inclusion criteria have been met, none of the exclusion criteria are present and fill out an Eligibility form. The infant will be assigned the next available pre-printed randomization number from the randomization log for the appropriate GA stratum. Research staff will determine the treatment assignment corresponding to the randomization number by calling the research pharmacy staff that is available 24/7. As confirmation of randomization, an order form documenting the randomization will be placed in the infant's electronic medical record (Appendix VII [Study Flow, Table A1]).

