An *a priori* computer-generated stratified block randomization list will be used to assign patients to each of the 4 parallel fixed dosing schedules (allocation ratio 1:1:1:1, total subjects = 120). To ensure randomization of equal number of subjects to both nebulizers, block size of 8 will be used. To ensure equitable representation of gestational ages, GA stratum-specific randomization lists will be generated. Stratified block randomization will ensure balanced and independent distribution of participants within each dose group, avoid systematic differences between dose groups with respect to known or unknown confounding baseline variables, remove selection bias and control temporal trends^{2,62-66}. The balance resulting from blocked stratification can improve the power of trials by reducing unwanted variation, reduce Type I and II error rates, increase efficiency, and improve subgroup analyses.

The structure of Table 10 shows breakdown of the sample by confounding variables in rows (GA [stratifying factor] & nebulizer type [blocking factor]) with columns representing treatment groups. Therneau showed that balance in covariates begins to fail when the number of blocks approaches half the sample size (n/2)^{64,67}. Therefore studies using stratified assignment should not attempt to balance on

Table 10: Stratified Block Randomization of Sample

GA Group (Strata)	Nebulizer Device (Blocks)	Dosing Schedule			
		I	II	III	IV
24 0/7 – 28 6/7 (Extremely PT) ⁶¹	MiniHeart	5	5	5	5
	AeroNeb	5	5	5	5
29 0/7 – 32 6/7 (Very PT)	MiniHeart	5	5	5	5
	AeroNeb	5	5	5	5
33 0/7 – 36 6/7 (Moderately PT)	MiniHeart	5	5	5	5
	AeroNeb	5	5	5	5
Total		30	30	30	30

more than 2 to 3 important factors. In this study we have balanced 2 important factors (GA, nebulizer type); the resulting number of blocks (3 GA strata x 2 nebulizers x 4 dosing schedule groups=24) is <n/2 (120/2=60).

Multiple births, common in this premature population, will be randomized independently and not as a unit as the latter can lead to bias in the randomization process.

1.1.4.7. Allocation Concealment:

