The randomization list with treatment assignments corresponding to randomization numbers will be generated by the study statistician not involved in screening or enrollment of study subjects. The research pharmacist, also not involved in screening or enrollment, will receive the list and keep it concealed. For each infant enrolled, the research staff will obtain the treatment assignment corresponding to the infant’s randomization number from the research pharmacist by phone thus eliminating allocation bias⁶⁸.

1.1.4.8. Blinding:

All enrolled infants will receive active medication; only the research staff and pharmacist will be aware of the infants’ assigned group. Study medication will be reconstituted by research staff in a designated private space in the NICU. The clinical caregivers and subjects will be blinded to dose and dilution, although an experienced clinical caregiver may be able to guess the dose and dilution. Research staff monitoring the enrolled infants during study intervention will collect objective data thus minimizing bias. It is not possible to blind nebulizers as they are of very different configurations and covering them will interfere with monitoring during clinical care. Infants will remain on their allocated nebulizer device for the duration of the study.

1.1.4.9. Clinical Care of Enrolled Infants:

The attending neonatologist and clinical team will make all decisions for initiation of NIV support and need for intubation and/or intratracheal surfactant instillation. Consensus guidelines have been agreed upon by clinical staff based on previously published studies for consistency^{7,33,34,69-74}.

Suggested initial and maximum settings for NIV support are provided although clinicians may individualize care (Table 11)^{33,34,74}. Escalation of NIV will be recommended for increasing FiO₂ (>10% from baseline), partial pressure of CO₂ (PCO₂, >10 mmHg from baseline), or clinical respiratory distress. Weaning will be recommended for SpO₂ and PCO₂ maintained at 90-95% and <65 mmHg respectively for 4 hours in the absence of significant clinical signs of respiratory distress³⁴.

Table 11: Suggested initial and maximum settings for NIV support

Settings	NIPPV		NCPAP		HFNC	
	Initial	Max	Initial	Max	Initial	Max
rate bpm	10	40				
PIP (cm H ₂ O)	10 above PEEP	18				
PEEP (cm H ₂ O)	5-6	8	5-6	8		

FiO2 % to maintain SpO2	90-95%	90-95%	90-95%	90-95%	90-95%	90-95%
Ti Seconds	0.3-0.5	0.3-0.5				
Flow LPM	8-12	8-12	8-12	8-12	2-3	5-6

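### A fixed, published block of 8 and unblinded enrolling staff make upcoming assignments partly predictable, so the claims that selection and allocation bias are removed go too far

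*Combined protocol and SAP*

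**What the plan says.** - Section 1.1.4.6 uses separate lists for three gestational-age strata, with "allocation ratio 1:1:1:1, total subjects = 120", and one block size: "To ensure randomization of equal number of subjects to both nebulizers, block size of 8 will be used". Section 1.1.1 gives the same purpose: "Equitable representation of two FDA-approved nebulizers will be achieved by using block sizes of 8".
- Table 10 plans 5 infants in every stratum-by-nebulizer-by-schedule cell (row "MiniHeart 5 5 5 5"). The text counts the cells as "3 GA strata x 2 nebulizers x 4 dosing schedule groups=24".
- Under section 1.1.4.1, research staff screen admissions, and "the research team will determine that all inclusion criteria have been met". The infant takes the next number in the stratum's log, and research staff phone the pharmacy for the assignment.
- Under section 1.1.4.8, "only the research staff and pharmacist will be aware of the infants" and their groups, and research staff make up the study drug. Clinical caregivers are blinded to dose and dilution but not to the nebulizer.
- Under section 1.1.4.7, the statistician who makes the list and the pharmacist who holds it do not screen or enrol. From the phone call the section concludes "thus eliminating allocation bias". Section 1.1.4.6 credits stratified blocking with taking selection bias away, and section 1.1.1 says the same of randomization.

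The supplied text mentions no variation in block size and does not say that the size is kept from enrolling staff.

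**The concern.** Concealing the list protects assignments only while they cannot be worked out from those already revealed. Here the block size is fixed and printed in the protocol, and the group that enrols is the group that learns each assignment. Towards the end of a block, the remaining possibilities are few.

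The protocol's own figures suggest why staff might have a preference. Schedule I comes to 4 + 4 = 8 ml/kg and Schedule IV to 8 + 16 = 24 ml/kg (section 1.1.4.3). At the jet nebulizer's stated 8 ml/hr (section 1.1.4.4 b), that is 1 against 3 hours per kg for each dose. Section 1.1.4.4 a expects the devices to differ in clogging and in acceptance by bedside staff.

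If the decision or timing of enrolment responded to the expected assignment, the groups could differ in baseline severity. The comparisons affected would be those between schedules, doses and nebulizers, and the schedule and dose comparisons guide the choice for Phase III (sections 1.1.7.3 and 1.1.12, Aim 2).

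**Working it through.** **Table 10 reproduced.** 40 infants per stratum / 8 = 5 blocks. With each of the 4 x 2 = 8 combinations once per block, each cell holds 5, each schedule 3 x 2 x 5 = 30, and the total is 3 x 5 x 8 = 120. All agree with Table 10. The protocol does not state that each combination occurs once per block, but this is the only constant block composition that gives Table 10. The schedule and dose results below need only two of each schedule per block.

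**Assumption.** The guesser knows the block size and every earlier assignment in the stratum, and always names the likeliest remaining option. This gives upper bounds.

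**Best guess, block of 8**

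- Combination: with k places left the chance is 1/k. Sum of 1/k for k = 1 to 8 = 2.718; / 8 = 34.0% (chance 12.5%).
- Schedule, positions 1 to 8: 0.250 + 0.286 + 0.333 + 0.400 + 0.443 + 0.476 + 0.571 + 1 = 3.760; / 8 = 47.0% (chance 25%). For example, at position 7 the last two share a schedule with probability 1/7, giving 1/7 + (6/7)(1/2) = 0.571.
- Dose level, or nebulizer (4 and 4 per block): 4 + (2^8/C(8,4) - 1)/2 = 4 + (256/70 - 1)/2 = 5.329; / 8 = 66.6% (chance 50%).

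**Known with certainty, block of 8**

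- Combination: the last in each block, 1/8 = 12.5%, or 15 of 120 infants.
- Schedule: (1 + 1/7)/8 = 14.3%.
- Dose or nebulizer: (1 + 3/7 + 6/42 + 6/210)/8 = 1.6/8 = 20%.

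The first assignment in a block is unpredictable. From the sixth on, at least one schedule is always ruled out.

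**Larger blocks, size still known** (exact enumeration for the combination's best guess; the formulas above for the rest)

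| Block | Best guess, combination | Best guess, dose or nebulizer | Combination certain |
|---|---|---|---|
| 8 | 34.0% | 66.6% | 12.5% |
| 16 | 4.74/16 = 29.6% | 62.8% | (1 + 1/15)/16 = 6.7% |
| 24 | 6.52/24 = 27.2% | 60.8% | 4.5% |

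Larger blocks roughly halve the certain assignments, or better, but lower the best-guess rates only modestly.

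**Current targets.** Section 1.1.10 moves the two higher strata from 40 to 60 infants each, then adds 40 more across them. 60/8 = 7.5, so no set of whole blocks in multiples of 8 ends at 60, and exact cell balance no longer follows there.

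**The case against.** Several points on the other side stand.

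- **Knowledge may be incomplete.** The documents describe research staff as a group. They do not say that each person who enrols sees every assignment on all three lists. A reader might infer that staff can simply foresee the sequence; the text supports only partial prediction, at most at the rates above.
- **Discretion is shared.** The clinical team decides on starting NIV and on intubation (section 1.1.4.9), must intend to give surfactant if the infant is intubated, and gives permission to approach parents. It is blinded to dose and dilution, although section 1.1.4.8 concedes that experienced caregivers may guess. Seeking consent antenatally or soon after admission limits steering by timing. Research staff still confirm eligibility, so some discretion remains.
- **The main efficacy test is not affected.** All infants receive active drug, and the whole-cohort comparison with 50% does not depend on who received which schedule. Section 1.1.12 already treats the between-schedule comparisons as probably underpowered.
- **Part of the remedy is planned.** Baseline data will be reported by schedule, CRIB and respiratory distress scores are collected, a screening log exists, and exploratory models adjust for gestational-age group, nebulizer and NIV mode.
- **It is late.** The document is dated 07-31-2017, and the higher strata met their goals in December 2016. New lists reach only the infants still to come.

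These points limit the consequence. They do not make the two claims true, because neither the phone call nor the separate list-holder stops staff from using assignments already revealed.

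**Conclusion.** The design leaves upcoming assignments partly predictable, and the statements that it takes away selection bias and allocation bias are not properties of it. With complete tracking within a stratum, best-guess success is at most 34% for the combination, 47% for schedule and 67% for dose or nebulizer, and one combination in 8 is certain. The combination figures rest on each combination appearing once per block. The nebulizer figure also assumes that the device is assigned from the list, as sections 1.1.4.6 and 1.1.4.8 indicate; section 1.1.4.4 a says that the device is not mandated, and these passages need reconciling.

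Two stronger readings are not supported. The first is that enrolment was in fact steered: the documents contain no evidence of it, and a guess rate is not an estimate of bias in an outcome. The second is that the trial's overall efficacy conclusion is compromised: exposure is confined to comparisons between schedules, doses and nebulizers.

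**What to change.** 1. In sections 1.1.4.6 and 1.1.4.7, say that the scheme *reduces* selection and allocation bias, and align section 1.1.1. State the residual predictability as a limitation of the schedule, dose and nebulizer comparisons.
2. For infants still to be randomized, including the extensions in section 1.1.10, have the study statistician generate lists with randomly varying block sizes in multiples of 8. Size them to the current stratum targets, not the original 40, and let them run past a target that is not a multiple of 8.
3. Keep the new sizes out of every document that enrolling staff hold. This matters because blocks of known size 16 or 24 still leave a 30% or 27% best-guess rate for the combination.
4. Extend the baseline reporting planned by schedule to nebulizer, including CRIB and respiratory distress scores, and report screened-but-not-enrolled infants from the existing log.

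Items 1 and 4 cost little and can be done at any stage. Items 2 and 3 need one new set of lists. Their downside is a slightly larger possible imbalance if a stratum stops part-way through a block, and they do nothing for infants already randomized.
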